# **Role of Sponsor and Funder**

Manchester University NHS Foundation Trust is acting as sponsor for this study and is assuming overall responsibility for the initiation and management of the

Title: Costs and benefits of Magtrace® in breast surgery Protocol V1 Date 03/08/2022

IRAS 293053 Page 2 of 45

study. The Trust will provide permission to conduct the research and monitor the progress of that research. The research team all hold substantive or honorary contracts with the Trust and therefore the sponsor has influence over all aspects of the study design, conduct, data analysis and interpretation, manuscript writing, and dissemination of results which are the responsibility of the research team.

The funder Endomagnetics Ltd have provided funding to conduct the trial, reviewed the study design, a representative will sit on the trial steering committee and be sent a copy of the results at the end of the trial.

# **Study Summary**

Title:	Cost Effectiveness and benefits of Magtrace® versus Technetium in sentinel node biopsy for breast cancer				
Short title:	Cost benefit of Magtrace® in breast surgery				
Medical Device:	Magtrace®				
Phase of trial:	IV				
Objectives:	Primary Endpoint				
	Cost effectiveness of Magtrace® compared to Technetium in the identification of sentinel nodes in breast cancer.				
	Secondary Endpoint:				
	Patient time spent in hospital and in transit in total				
	over pre-operative and perioperative journey				
	Patient anxiety on day of surgery – as measured				
	using State trait anxiety questionnaire STAI-Y given				
	on ward on morning of surgery.				
	
 
Number and length of patient hospital visits –
 
				
	comparing preoperative visits (clinic visits,				
	preoperative assessment, tracer injection visits, ward				
	visits and operative visits).				
	Safety of Magtrace® and efficacy – adverse events				
	relatable to tracers, number of nodes removed,				
	number of nodes containing tracer, % of patients with				
	detectable tracer in the axillary sentinel nodes, can				
	surgeons differentiate Magtrace® and Magseed signal®.				
	Cost per episode and for total care.				
	
 
Surgical start time, days of week of operating, and
 
				
	delays to getting patient to theatre. Delays will be				
	dolays to gotting patient to theatre. Delays will be				

	recorded by asking the theatre team directly pre-
	operatively whether they had to wait for the patient to
	arrive, and what the reason was, and also whether
	the list had to be rescheduled/ moved to
	accommodate a delay.
	To map the current pathways of patient care.
	Evaluation of the key aspects of care pathways
	important to patients and healthcare professionals in
	the management of breast cancer.
	Preferences/overall satisfaction with care package
	for Magtrace vs. Technetium, from the perspective of
	patients and healthcare providers.
Type of trial:	Single site, case control study investigating the healthcare
	costs of Magtrace®, and a discrete-choice qualitative
	experiment of the perceived value of Magtrace® vs. the
	current standard of care
	41 I

## Trial design and methods:

Magtrace® is a Superparamagnetic iron oxide (SPIO) nanoparticles, and is a novel tracer for detection of sentinel lymph nodes (SN) in patients with breast cancer. Magtrace®, when used in conjunction with the Sentimag® System (base unit and probe), can be used as a guide for the surgeon to facilitate excision of the sentinel lymph nodes in breast cancer surgery.

The magnetic tracer is proven to be non-inferior to the standard method of sentinel node detection in two meta-analyses [ (Teshome M, 2016 May, 23(5))][ (Karakatsanis A, 2016 Jun; 157(2))]. This Phase IV study is designed to assess the cost-effectiveness of using the CE marked Magtrace® device in the UK healthcare system.

The study will be carried out two parts; Part I - a health economic analysis informed by a time in-motion study, and, Part 2 – a Discrete-Choice Experiment (DCE) to elicit preferences for, and satisfaction with Magtrace vs. the current

standard of care. The two methodologies would occur in parallel and not sequentially.

#### Methods:

- 1. Part 1. Cost-implications and efficiency gains from using Magtrace® vs the current standard of care: A time-in-motion study
- Part 2. Managing Breast Cancer: What matters when treating breast cancer? Focus Group and Survey
   Patient and Healthcare provider preferences towards the management of

breast cancer: A Discrete-choice experiment

Trial duration per	8 weeks maximum			
participant:				
Estimated total	14 months			
trial duration:	T THORISTO			
Planned trial sites:	Single Centre – Wythenshawe Hospital			
Total number of	Part 1: 50 (5-10 pilot patients, 20 under Magseed, 20 under			
participants	the current SOC).			
planned:	Part 2: Managing Breast Cancer: What matters? A focus-group, will include 5-10 patients to help design the discrete choice experiment.			
	Managing Breast Cancer: What Matters? Survey. Discreet Choice Experiment will include:			
	150 patients			
	50 healthcare professionals			
Part 1 Main	Part 1 Inclusion:			
inclusion/ exclusion criteria:	Participant is willing and able to give informed			
	consent for participation in the study;			
	Female, aged 18 years or above;			
	Diagnosed with breast cancer (invasive) requiring			
	Magseed® localisation and sentinel node biopsy			

- Willing to allow his or her General Practitioner and consultant, if appropriate, to be notified of participation in the study;
- Undergoing breast conserving surgery with sentinel node biopsy
- Surgeons may only operate on the Magtrace arm of the study if they have completed a minimum of five training cases with Magtrace.

#### Part 1 Exclusion criteria:

- Patients with a Pacemaker or implanted device in the chest wall;
- Patients who are pregnant or lactating;
- Patients who have received Magtrace® (iron oxide) injection in the previous six months;
- Patients with previous ipsilateral axillary surgery
- Patients whose breast and axillary surgery are not due to be performed synchronously.
- Patients following neoadjuvant chemotherapy
- Patients who require MRI follow-up of the ipsilateral breast in the year following surgery (as Magtrace® may interfere with MRI)
- Patients requiring an interpreter
- Patients involved in current research or have recently been involved in any research prior to recruitment

•

# Part 2 inclusion/ exclusion criteria

Part 2 Inclusion criteria: – mixed recruitment of HCP and patients

- Over 18
- Must be fluent English speaker.

HCPs- must be involved in the day-to-day care of patients surgical pathways.

Patients – can be naïve to the surgical pathway or have experience of having undergone breast conservation surgery within the last two years.

Part 2 Exclusion criteria:

• Under 18

# 2. Glossary of Terms

AE Adverse Event
AR Adverse Reaction
CI Chief Investigator
CRF Case Report Form

CT Clinical Trials

DCIS Ductal carcinoma in situ

DSMB Data Safety Monitoring Board

GCP Good Clinical Practice
GP General Practitioner
ICF Informed Consent Form

MRI Magnetic resonance imaging

NHS National Health Service
HRA Health Research Authority
PI Principal Investigator

PIL Participant/ Patient Information Leaflet

R&I NHS Trust R&I Department REC Research Ethics Committee

SAE Serious Adverse Event SAR Serious Adverse Reaction

SIL Subject Information Leaflet (see PIL)
SOP Standard Operating Procedure

SUSAR Suspected Unexpected Serious Adverse Reactions

TMF Trial Master File U/S Ultrasound

WLE Wide Local Excision (lumpectomy surgery)

## 3. Background and Rationale

## **Breast Cancer**

Breast cancer is a heterogeneous disease, with great diversity in the site, size and progression of tumours. Some are palpable and discovered by the patient, though many are first detected during mammogram screening. For such cancers, localisation is necessary prior to surgery, to guide surgeons to the target excision site. During surgery for breast cancers, surgeons will often perform a sentinel node biopsy to check the draining lymphatic glands for signs of early cancer spread.

#### Iron Oxide Use in Breast Surgery

Several studies have investigated the use of liquid injections of iron oxide (Magtrace®) rather than traditional radioisotope and blue dye injections, in sentinel node identification. Following iron oxide injections, a handheld magnetometer (Sentimag®) was used to detect the location of iron oxide in the lymph nodes. All studies concluded that iron oxide particles performed equally as well as standard radioisotope & blue dye injections in sentinel node identification, demonstrating potential for more widespread use of the technique. Magtrace® can be injected up to seven days prior to the date of surgery which allows the injection to be given simultaneously when the patient attends for a pre-existing hospital visit in the week prior to surgery (e.g. coinciding with a pre-operative anaesthetic assessment or at the same time as placement of the Magseed®) or on the day of surgery. Currently we perform this most often on the day of surgery and this will be the intention during this study. If the patient has received localisation of the cancer (by Magseed®) prior to the date of surgery and Magtrace® for the sentinel node then the patient requires no further preparations prior to surgery. The patient can arrive in the hospital at the scheduled time and be prepared for theatre. Technetium injections have by contrast, a half-life meaning that injection has to occur in the 16 hours prior to surgery. This can be given on the day prior to surgery (Two day protocol), but this means an extra visit for the patient, or on the day of surgery (but this means the patient has to have an injection on the morning of surgery and have two hours for the technetium to move to the nodes prior to surgery). Logistically this means a challenge to get the patient ready in time for the first half of a morning list as the injection should be done two hours prior to surgery, and is even more challenging on a Monday morning as

Technetium is not available for weekend injection in most sites. Technetium is also in short supply worldwide and is becoming increasingly difficult to source. Magtrace® has the potential to make the perioperative pathway simpler for the patient, less stressful around the time of surgery and to avoid delays in the perioperative setting.

#### Wire Guided Localisation

Traditionally, localisation involves radiographic-guided insertion of a wire into the breast, with positioning of the wire tip at the centre of the lesion. However, this procedure carries several logistical limitationsi,ii stemming from the fact that wire localisation must be performed on the day of surgery. This is to minimise risk of wire migration or dislodgementiii, a significant possibility due to the external section of wire left protruding from the breast. Same-day appointments demand excellent coordination between radiological departments and operating theatres to ensure that disruption to procedure scheduling is minimised. Delays may result from technically difficult proceduresiv, leading to over-running radiology appointments that have a knock on effect on operating lists.

Another limitation of wire guidance occurs because the wire directs surgeons along a linear route. Lesions are found at a point along the wire, though it can be difficult to determine how far along they are found. For this reason, surgeons making initial incisions may be dictated by the visual trajectory of the wire, rather than the location of the lesion. This can lead to excessive dissection and sub optimal cosmetic results.

#### Magseed® Magnetic Localisation

The localisation method with which this project is concerned has similar principles to radioactive seed localisation) RSL. However, instead of radioactive seeds, a soft magnetic seed called Magseed®, is placed into the breast. The seed is similar to a biopsy clip and can be detected using a handheld magnetometer called Sentimag®. The Sentimag® probe emits an alternating magnetic field that detects the magnetic response of the Magseed® seed. The magnetometer produces an audible response when held close to the Magseed® seed and can be used by surgeons to locate target excision sites. Magseed® is inserted well before the operation, ideally tied in with a pre-operative anaesthetic appointment, for patient convenience.

Magseed® is a novel method of localisation that has been validated in Manchester for use in breast conservation surgery. It is widely adopted across the UK in 45 units (Nov 2019) and has been audited nationally in an audit led in Manchester to compare its performance to wire localisation.

## Summary of Localisation and sentinel node Techniques

The coordination and scheduling difficulties encountered in wire guided localisation, alongside the logistical and safety issues of radioisotope usage, highlight a requirement for further innovation and acquisition of new technologies in the field of localisation of breast lesions and sentinel nodes. Magseed® is currently used as the standard of care in Manchester University NHS Foundation Trust for lesion localisation. Technetium +/- blue dye is currently used as the standard for care for sentinel node localisation. Part 1 of this study would aim to assess the cost-effectiveness of using Magtrace® for sentinel node localisation compared to a control group of patients receiving Technetium. Part 2 will be a Discrete choice experiment for patients and health care professionals to ascertain the values of Magseed® and Magtrace® compared to wire localisation and Technetium sentinel node localisation.

## 3.1 Study Population

Adult women with capacity to consent who have a proven breast cancer requiring breast conserving surgery requiring localisation with a Magseed®, and who also require a sentinel node biopsy on the same date.

#### 3.2 Potential Risks to Patients

- All processes and technologies have previously been proven to be efficacious and effective.
- Technetium sentinel node injection is often combined with a blue dye to
  increase nodal yield. The blue dye has a small risk of anaphylaxis of
  approximately 1 in 10,000 and can stain the skin of the breast blue for several
  months. Magtrace® does not have a risk of anaphylaxis but can stain the skin
  of the breast brown for several months post-operatively.

Title: Costs and benefits of Magtrace® in breast surgery Protocol V1 Date 03/08/2022

Magtrace® is used as a single tracer whereas Technetium is either used as a single tracer or as a dual tracer with blue dye. Both methods are standard of care and their utility is dependent on the availability of one of the two dyes.
 I.e. if technetium not available Magtrace is used and vice versa. The number of nodes removed during Magtrace® localisation is slightly lower than that with Technetium, as proven on Meta-analysis (on average 1.9 nodes removed vs 2 with Technetium). This difference in tracer performance has not been shown to be clinically relevant or to increase the risk of lymphoedema in patients' index arm's as a result of removing slightly more lymph nodes in the case of Technetium.

#### 3.3 Potential Benefits

The potential benefits of using Magtrace® will be in simplifying the patient pathway in the pre-operative period. Magtrace® will be given on the day of surgery, whereas Technetium would be given on the day of surgery or the day before. This means around the time of surgery there will be less stress for the patient, they will be ready to have their surgery at any time of the day (rather than having to wait until they have a Technetium injection). Technetium requires aliquoting out from the Christie and transporting across to the Nuclear medicine department on a daily basis, and following radioactive licences, must be given by two trained professionals in a very controlled manner. Magtrace® can be given by any trained member of staff without the need for ARSAC radioactivity licences. It will negate the need for the complex process of transferring the Nuclear medicine across the city and the need for staff to make up the injections every morning and give them to patients. Magtrace® will therefore simplify the pathway and remove multiple steps freeing up staff for other jobs. Magtrace® will make theatre scheduling in the morning easier as any patient will be available for theatre, potentially making less waiting for theatre staff and more efficient operating. It is unlikely that extra cases will be done as a result of the change but it may avoid overruns and delays in theatre.

## 4. Trial Objectives and Design

## 4.1. Trial Objectives

# **Primary and Secondary Endpoints/Outcome Measures**

## The Primary Endpoint:

Cost effectiveness of Magtrace® compared to Technetium in the identification of sentinel nodes in breast cancer. (Part 1).

#### Secondary Endpoints

- Patient time spent in hospital and in transit in total over pre-operative and perioperative journey (Part 1)
- Patient anxiety on day of surgery as measured using State trait anxiety questionnaire STAI-Y given on ward on morning of surgery (Part1).
- Number and length of patient hospital visits comparing preoperative visits (clinic visits, preoperative assessment, tracer injection visits, ward visits and operative visits) (Part 1).
- Safety of Magtrace® and efficacy adverse events relatable to tracers, number of nodes removed, number of nodes containing tracer, % of patients with detectable tracer in the axillary sentinel nodes (Part 1), can surgeons differentiate Magtrace® and Magseed signal®.
- Cost per episode and for total care (Part 1).
- Surgical start time, days of week of operating, and delays to getting patient to theatre. Delays will be recorded by asking the theatre team directly preoperatively whether they had to wait for the patient to arrive, and what the reason was, and also whether the list had to be rescheduled/ moved to accommodate a delay (Part 1).
- To map the current pathways of patient care (Part 1).
- Evaluation of the key aspects of care pathways important to patients and healthcare professionals in the management of breast cancer (Part 2).
- Preferences/overall satisfaction with care package for Magtrace vs.
   Technetium, from the perspective of patients and healthcare providers (Part 2).

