## Study design (Part 1)

For Part 1, time-driven and activity-based costing (TDABC) will be utilised. TDABC is a bottom-up approach to healthcare pathway mapping and costing, which records pathways observed during routine clinical practice, identifies all points and durations of interaction with healthcare providers therein; and assigns time-dependent costs to each constituent. This method of costing is far more granular than reference costingv and enables not only an estimation of the economic impact of care pathways, but also the implications for healthcare professionals and service planning. This is due to the ability to monitor the extent of patient-HCP interactions, and to determine the true 'time cost' of existing and novel care pathways. The costs of non-time-dependent activities, including tariff-based ancillary investigations, radiography, and outpatient services, are subsequently added, based on reference costs, to provide a representative activity-weighted cost per completed treatment episode.

This approach is common in health service research.vi The methodology is the most thorough and comprehensive way to determine the real-world impact of Magtrace® on both patient flow, and clinical involvement with patients vs. the current standard of care, highlighting differences in both resource use and care pathways therein. Highly accurate and internally valid, this approach would enable the comparison of both the efficiency of breast cancer excision, and the workload of healthcare providers, whether clinical, clerical, or simply observation. Combined, these factors will combine a holistic estimate of the expected difference between existing care, and a switch to widespread use of Magtrace®.

Prior to recruitment, research staff will begin by mapping the current pathways for breast cancer excision at Wythenshawe Hospital and providing a preliminary

assessment of the workload of all members of staff involved in the patient pathway, from the decision-to treat appointment through to completion of surgery. Using a Delphi-approach, and coordination with staff from the Nightingale centre they will determine an outline of the basic resources involved, including staff costs (time, grade), radiography, inpatient and add-on costs.

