It will be the responsibility of the research assistants to provide a 'learned' assessment, of what they believe represents a 'typical' pathway at the Nightingale centre. A multidisciplinary team will then assess the validity of this pathway and voice any concerns/objections/potential additions. Once an accurate representation of the existing care pathway has been generated (as agreed by research staff and clinical leads), this will be pilot tested among a group of 10 patients (5 current SOC and 5 Magtrace), in order to ensure that all relevant points of interaction with healthcare staff, and utilisation of health services, are captured, the pathway will be amended as necessary. Using a stopwatch, research staff would have the ability to consent and then actively monitor (shadow around the hospital) a group of ~20 patients in each treatment group (Magtrace® vs. routine care using Technetium nuclear medicine). It is critical prior to recruitment that key covariates and factors likely to influence not only outcomes, but also health economic factors of care are identified. These factors will require consideration before randomisation to Magtrace or routine care, with randomisation recommended to take place using sealed envelopes in blocks of ten. If imbalances in key covariates occur following randomisation, adjustment of health economic outcomes will be performed to mitigate these imbalances using gold-standard two-stage bootstrapping for costeffectiveness analyses.

[figure not shown]
Once data is collected for 20 patients undergoing Magtrace, and 20 patients undergoing routine care, it will be possible to multiply NHS resource utilisation by representative NHS unit costs (staff salaries per minute, radiography, inpatient, nuclear medicine) and determine the array of health economic outcomes listed above. The result will be a health-economic comparison of Magtrace® over Technetium nuclear medicine (Figure 1). Sensitivity analyses will be performed on this dataset to measure the robustness of the findings to changes in the values of the parameters measured during the TDABC stopwatch exercise. Rather than relying on point-estimates, this will enable the derivation of credible intervals, and determine

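### Theatre delay is recorded with no length of wait, so theatre staff waiting has no specified quantity in Part 1's per-minute costing

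*Protocol*

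**What the plan says.** Protocol section 4.1 (Secondary Endpoints) names the endpoint as "Surgical start time, days of week of operating, and delays to getting patient to theatre" and then fixes the method: "Delays will be recorded by asking the theatre team directly preoperatively whether they had to wait for the patient to arrive". The same sentence continues "and what the reason was, and also whether the list had to be rescheduled/ moved to" make room for a delay. The Study Summary and section 7.2 repeat the item. It therefore yields one clock time (surgical start), the day of the week, whether the team waited, why, and whether the list changed.

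Section 4.2, Study design (Part 1), describes a costing that "identifies all points and durations of interaction with healthcare providers therein; and assigns time-dependent costs to each constituent". Research staff with a stopwatch are to "actively monitor (shadow around the hospital) a group of ~20 patients in each treatment group", and the resources used are then multiplied by unit costs that include staff pay per minute.

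Section 3.3 gives the expected effect on theatre: easier morning scheduling, "potentially making less waiting for theatre staff and more efficient operating". It adds that extra cases are unlikely.

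**The concern.** A delay is a length of time, yet none of the listed items is a length. Surgical start time becomes lateness only when set against a scheduled or team-ready time, and neither is listed. The stopwatch does not fill the gap as described, because it follows the patient and times contacts between patient and staff. A theatre team waiting for a patient who has not arrived is not such a contact.

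Two things are at stake. First, the cost comparison behind the primary endpoint lacks a stated input for a saving that the protocol itself anticipates. Since section 3.3 does not expect more cases per list, a theatre-side saving would show mainly as time. Section 4.2 then extrapolates from the 40 patients to annual caseload and return on investment, which carries the gap forward. Second, a yes/no answer scores a 2-minute wait and a 60-minute wait alike.

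**Working it through.** **Inputs.** From the protocol: about 20 patients per arm, 1:1 (section 4.2). Not given for this endpoint: test, alpha, power, delay rates, length of delay or team size (sections 10.1 and 10.3 only refer back). There is thus no stated figure to reproduce. Everything below assumes two-sided 5% and is illustration only.

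**Step 1. What the costing needs.**

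Cost of waiting = minutes waited × staff waiting × cost per staff-minute.

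The third factor is provided for in section 4.2, and staff grades and time come from the pathway mapping. The first factor has no specified source. With an assumed team of 4 to 7, one 30-minute wait is 30 × 4 = 120 to 30 × 7 = 210 staff-minutes.

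**Step 2. Power if minutes shift as a normal variable.** With d the difference in SD units:

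- Minutes: power = Φ(d√(n/2) − 1.96). At n = 20, d = 0.8: Φ(2.530 − 1.960) = 72%. At d = 1.0: Φ(3.162 − 1.960) = 89%.
- Yes/no: power = Φ{[|p1 − p2| − 1.96√(2p̄(1 − p̄)/n)] / √[(p1(1 − p1) + p2(1 − p2))/n]}, where p̄ is the mean of p1 and p2. Cutting the same variable midway between the arm means at d = 0.8 gives p1 = Φ(0.4) = 0.655 and p2 = 0.345, so (0.311 − 0.310)/0.150 ≈ 0 and power is 50%. Cutting at the control median gives 48%. At d = 1.0 the figures are 69% and 64%.
- At d = 0.9, 80% power needs 2(1.960 + 0.842)²/0.81 = 19.4, so 20 per arm for minutes, against 32 (midpoint cut) to 35 (control-median cut) for yes/no.

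This model favours minutes, because it also credits early arrival, which is not waiting.

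**Step 3. Minutes waited, zero if none.** Simulation with 3,000 runs per row, 20 per arm; waits among delayed patients are log-normal with log-SD 0.8. The mean wait among delayed patients is median × exp(0.8²/2) = median × 1.377. Minutes per patient are that mean times the delay frequency; for example 0.5 × 30 × 1.377 = 20.66.

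| Delayed, control v Magtrace | Median wait, min | Mean minutes per patient | Difference | Chi-square on yes/no | Mann–Whitney on minutes | Welch on minutes |
|---|---|---|---|---|---|---|
| 50% v 20% | 30 v 30 | 20.66 v 8.26 | 12.4 | 53% | 48% | 29% |
| 50% v 20% | 30 v 15 | 20.66 v 4.13 | 16.5 | 52% | 62% | 58% |
| 50% v 40% | 30 v 10 | 20.66 v 5.51 | 15.1 | 9% | 28% | 49% |
| 50% v 50% | 30 v 10 | 20.66 v 6.89 | 13.8 | 5% | 16% | 38% |

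The quantity to be costed is similar in all four rows, about 12 to 17 minutes per patient, while the power of the yes/no comparison runs from 53% down to 5%. In the last row the yes/no record would show no difference, although 13.8 minutes per patient, or 13.8 × 4 = 55 to 13.8 × 7 = 97 staff-minutes, separate the arms. In the first row yes/no is the best of the three tests.

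**The case against.** A reader might infer three stronger claims. The protocol supports none of them.

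- *Delay is recorded purely as yes/no.* It is not: the reason, the list change, the start time and the day are also taken, and nothing forbids noting a length. What stands is that no length is asked for.
- *Idle theatre time cannot be costed.* Too strong. Section 4.2 says the costing covers staff workload broadly, up to the end of surgery. The shadowing researcher could see the patient arrive. The pathway may be amended after a 10-patient pilot. The schedule in section 6 has a row for data collection in theatre at Visit 2, and the CRF is still to be developed (section 15.1). These make recording minutes feasible, but do not provide for it. The pilot's stated aim is to capture staff contacts and service use, and waiting for an absent patient is neither.
- *The endpoint loses power.* Not in general. The protocol claims no power for this item, one of nine secondary endpoints, and every figure above rests on assumed distributions. Section 3.3 expects patients to be ready at any time, which suggests fewer delays rather than shorter ones. In that case yes/no does as well or better, and replacing it with a comparison of means would cost about 24 points (53% against 29%).

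It could also be said that the analysis plan, which is not at hand, will deal with this. It can choose the analysis, but it cannot recover times that were never taken.

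**Conclusion.** The point holds as a gap in measurement. The stated delay record contains no duration and no reference time from which one could be derived, so in a per-minute costing the theatre waiting that section 3.3 hopes to reduce has no specified quantity. This does not depend on any distributional assumption. Its size does: with an assumed 4 to 7 staff, each 30-minute wait is 120 to 210 staff-minutes.

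The statistical half is conditional. Yes/no cannot detect a difference in length alone (about 5% power, against 16% to 38% for minutes in the case tried), but the gain from minutes can be nil or negative when only frequency differs. The case for change therefore rests on the costing, and on the fact that yes/no can be derived from minutes but not the reverse. It is a cheap improvement to a secondary endpoint that feeds the primary cost comparison.

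**What to change.** In the Study Summary, section 4.1 and section 7.2, add to the delay item the scheduled time, the time the theatre team was ready and the time the patient arrived in theatre. The research staff already shadowing the patient should record them. As they are with the patient, they can get the team-ready time from the theatre team when asking the existing question.

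Derive minutes waited, set to 0 if there was no wait, and define the starting point in advance (for example, the later of scheduled and team-ready time). Multiply the minutes by the number and per-minute cost of the staff waiting, and include the result in the Part 1 costing. Report mean minutes per arm and their difference with a bootstrap interval. Keep the proportion of cases with a wait as an analysed outcome, together with the reason and list-change items.

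The cost is a few extra timed CRF fields per patient and a small wording change in three places.

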## 6.1 Magtrace injection protocol

Magtrace will be injected by the operating surgeon on day of surgery. This injection will occur prior to surgery, on the admitting ward with massage of the area. If the patient arrives in the theatre suite before being seen by a surgeon, the injection will be given by the surgeon prior to general anaesthetic.

Prior to injection, the surgeon giving the injection must check the pre-operative mammograms and Magseed position. The Magtrace injection should be injected 2cm deep in the breast to avoid staining of the skin, and at a distance to the Magseed. This is to ensure that the Magseed signal is not confused with the Magtrace injection site.

Some examples are given in the Figure below;

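### The theatre-delay question is tied to the patient's arrival, so it counts a hold-up from same-day Technetium but can miss one from Magtrace injected after arrival

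*Protocol*

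**What the plan says.** The endpoint appears in the Study Summary and in sections 4.1 and 7.2 of the protocol. Its components are "Surgical start time, days of week of operating, and delays to getting patient to theatre". The recording rule has two items. The first is "asking the theatre team directly preoperatively whether they had to wait for the patient to arrive", together with the reason. The second is "also whether the list had to be rescheduled/ moved to accommodate a delay".

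On the Magtrace pathway, section 6.1 states: "Magtrace will be injected by the operating surgeon on day of surgery". The default place is the ward: "This injection will occur prior to surgery, on the admitting ward with massage of the area". There is a fallback: "If the patient arrives in the theatre suite before being seen by a surgeon, the injection will be given by the surgeon", before general anaesthetic.

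On the control pathway, section 3 (Iron Oxide Use in Breast Surgery) and section 4.2 put Technetium either on the afternoon before surgery or on the morning of surgery, with two hours allowed for it to reach the nodes. Section 4.2 adds that the surgeon may also inject blue dye at the time of surgery, at the clinician's discretion.

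**The concern.** The first item of the recording rule uses the patient's arrival in theatre as its reference point. Technetium is always given before that point. Magtrace may be given on either side of it. A recording rule fixed at arrival can therefore treat hold-ups caused by the two tracers differently.

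This matters because fewer perioperative delays are among the advantages that sections 3 and 3.3 expect from Magtrace, and this endpoint is where that expectation is tested. If delays due to one tracer are counted more completely than delays due to the other, part of any observed difference may reflect the wording of the question. The primary cost-effectiveness endpoint is not directly affected.

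**Working it through.** The protocol gives no rate, duration, effect size or power for theatre delay, so there is no figure to reproduce. The check is to trace each source of tracer-related delay through the recording rule.

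| Source of hold-up | Arm | Seen by the arrival question? | Seen elsewhere in the endpoint? |
|---|---|---|---|
| Same-day Technetium makes the patient late | Control | Yes | List item, if the list is moved; start time |
| Technetium given the afternoon before | Control | Not applicable: no same-day injection | Not applicable |
| Ward Magtrace injection makes the patient late | Magtrace | Yes | List item, if the list is moved; start time |
| Magtrace injected in the theatre suite after arrival | Magtrace | No | List item, only if the list is moved; start time, without a stated reference |
| Blue dye injected in theatre | Control | No | List item, only if the list is moved; start time, without a stated reference |

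Three features of the rule decide how much is lost.

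1. The reason is asked about a wait for arrival. If the theatre team correctly answers that there was no such wait, nothing prompts them to report a wait for an injection.
2. The list item is not tied to arrival, but it responds only to a delay large enough to move the list. A short wait before arrival is counted; a wait of the same length after arrival is not.
3. Surgical start time is recorded in both arms, but the endpoint names no scheduled time. A start time alone does not show whether, or by how much, the case was late.

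For scale only, take the planned 20 patients per arm and three assumptions that are not in the protocol: a share *s* of Magtrace patients is injected in the theatre suite, a share *h* of those injections holds up the start, and none of these hold-ups moves the list.

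Missed Magtrace delays = 20 × *s* × *h*

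- *s* = 0: 20 × 0 × *h* = 0 missed.
- *s* = 0.10, *h* = 0.5: 20 × 0.10 × 0.5 = 1 missed, or 1/20 = 5 percentage points.
- *s* = 0.50, *h* = 0.5: 20 × 0.50 × 0.5 = 5 missed, or 5/20 = 25 percentage points.

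These are gross figures for one arm. In the control arm, if a share *b* receives blue dye in theatre and a share *g* of those injections holds up the start, 20 × *b* × *g* delays are missed. The net distortion in favour of Magtrace is 20 × (*s* × *h* − *b* × *g*). It is zero when the two products are equal and changes sign if the dye term is larger. None of *s*, *h*, *b* or *g* is given.

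**The case against.** The endpoint is broader than the arrival question alone. It also asks for the reason, asks whether the list was moved and records surgical start time. A reader might infer that only waits for arrival are counted; the full sentence does not support that.

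Ward injection is the default for Magtrace, and if it runs late the patient arrives late and is counted just as a late Technetium patient would be. Only the fallback route escapes the question. The contrast is softened further by blue dye in the control arm, which is also given after arrival, and by the two-day Technetium protocol, which involves no injection on the day of surgery. All of this stands, and it narrows the point considerably.

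Research staff also shadow patients with a stopwatch, and the costing in section 4.2 covers contacts with healthcare providers, so an injection in the theatre suite might well be timed. That stands in part: the protocol does not say that these times feed the delay endpoint. A statistical analysis plan, not shown here, could define lateness against a scheduled time, but only if that time is collected.

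Two further inferences are tempting. One is that a surgeon would leave a running list to inject the next patient on the ward. No section says so, and such an absence would be recorded if it made the patient late or moved the list. The other is that section 3.3, where "Magtrace® can be given by any trained member of staff without the need for ARSAC radioactivity licences", contradicts section 6.1. It does not: section 3.3 describes who may inject, section 6.1 says who will in this study, and an operating surgeon is a trained member of staff.

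**Conclusion.** The point holds in a limited form. The arrival question counts a hold-up from same-day Technetium and can miss a hold-up from Magtrace injected in the theatre suite, unless the list is moved. Recorded start time does not close the gap while no scheduled time is named.

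The net bias probably favours Magtrace. That is a judgement: it assumes that the fallback route is used at least sometimes, that it sometimes holds up the start, and that discretionary blue dye does not offset it fully. The size cannot be determined from the protocol, and the 0 to 5 missed delays out of 20 shown above are only an illustration under assumed inputs.

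A reader might go further and infer that a favourable delay result would be produced by the definition alone. The documents do not support that, because the default Magtrace route is captured and no frequencies are given. This is a cheap improvement confined to a secondary endpoint.

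**What to change.** In the Study Summary and sections 4.1 and 7.2, define delay identically in both arms as any hold-up to the start of surgery, whether before or after the patient arrives. Record from clock times the scheduled start, the actual anaesthetic start and knife-to-skin. For each hold-up, record the cause from a short list: late arrival, tracer or dye injection, waiting for the surgeon, other. Keep the theatre-team question to supply the reason, and keep the list item as it is.

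The cost is a few extra time fields on the case report form and a change of wording in those sections. Observers with stopwatches already accompany the patients, so little extra effort is needed. The downside for the study's case is that the delay result may look less favourable to Magtrace.
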